## 12.4. Appendix 4: Study Phase and Treatment Emergent Flag for Adverse Events

### 12.4.1. Study Phase

Assessments and events will be classified according to the time of occurrence relative to study intervention period.

**Pre-Intervention** is defined as time prior to the first dose of study intervention.

**On-Intervention** is defined as time from first dose to last dose plus 30 days. If time of assessment or study intervention is not collected, the following assessment on the first dose date will be assumed to be taken prior to the first dose and therefore considered pre-intervention: ECOG, ECG, lab, and vital signs, and first dose date is considered on-intervention for AE and concomitant medication.

**Post-Intervention** is defined as any time post on-intervention window, i.e. date > last dose date + 30 days.

#### 12.4.1.1. Study Phases for Anti-Cancer Therapy

This table should be used for anti-cancer systemic therapy, anti-cancer surgical/medical procedures and radiotherapy.

Study Phase	Definition
Prior	If anti-cancer therapy start date is not missing and is before the first dose of study intervention OR If anti-cancer therapy start date is missing and: 
 
• The anti-cancer systemic therapy comes from the Prior Anti-Cancer Therapy eCRF page.
 
• The anti-cancer surgical/medical procedure comes from the Prior Medical/Surgical procedures eCRF page.
 
• The radiotherapy comes from the Anti-Cancer Radiotherapy eCRF page.
 

On Treatment	If anti-cancer therapy start date is not missing and is on or after the first dose and before the last dose of study intervention (if anti-cancer therapy start day is on the same day as first dose then anti-cancer therapy is assumed to have been taken/Performed after first dose) OR If anti-cancer therapy start date is missing and: 
 
• The radiotherapy comes from the Anti-Cancer Radiotherapy On Treatment eCRF page.
 

Follow-up	If anti-cancer therapy start date is not missing and is on or after the last dose of study intervention (if anti-cancer therapy start day is on the same day as last dose then anti-cancer therapy is assumed to have been taken/Performed after last dose) OR If anti-cancer therapy start date is missing and:

Study Phase	Definition
	
 
• The anti-cancer systemic therapy comes from the Follow Up - Anti-Cancer Therapy eCRF page.
 
• The radiotherapy comes from the Follow Up – Radiotherapy eCRF page.
 

#### 12.4.2. Treatment Emergent Flag for Adverse Events

Flag	Definition
Treatment Emergent	
For AEs (which are not SAEs and not AESIs) in GSK3745417 monotherapy cohorts:
 
 
• Monotherapy participants who do not crossover: Study Treatment Start Date <math>\leq</math> AE Start Date or pre-existing (prior to exposure) AE Worsening Date <math>\leq</math> Treatment Discontinuation Visit (TDV) or Study Treatment Stop Date + 30 Days if TDV is missing.
 
• Monotherapy participants who crossover: Monotherapy Study Treatment Start Date <math>\leq</math> AE Start Date or pre-existing (prior to exposure) AE Worsening Date <math>\leq</math> Monotherapy TDV or the earliest of (Monotherapy Study Treatment Stop Date + 30 Days, Crossover Date) if TDV is missing.
 
• AE Start Date is missing.
 
 
For AEs (which are not SAEs and not AESIs) in GSK3745417 + dostarlimab combination cohorts:
 
 
• Study Treatment Start Date <math>\leq</math> AE Start Date or pre-existing (prior to exposure) AE Worsening Date <math>\leq</math> TDV or Study Treatment Stop Date + 30 Days if TDV is missing.
 
• AE Start Date is missing
 
 
Note that AE worsening date is included in the definition of AE start date in the eCRF and so no programming is required.
 
For AEs (which are not SAEs and not AESIs) in GSK3745417 + dostarlimab crossover cohorts:
 
 
• (Crossover) Combination Study Treatment Start Date <math>\leq</math> AE Start Date or AE Worsening Date for AE that started during the GSK3745417 monotherapy cohort <math>\leq</math> (Crossover) Combination TDV or (Crossover) Combination Study Treatment Stop Date + 30 Days if TDV is missing.
 
• AE Start Date is missing
 
 
Note, if a participant has an AE while on monotherapy and crosses over to combination therapy prior to the AE resolving:

Flag	Definition
	
 
• If the AE does not worsen, the AE will only be counted in the monotherapy cohort.
 
• If the AE does worsen, then the AE will be counted in both the monotherapy cohort and the crossover combination cohort.
 
 
Note that TDV date is taken as the latest TDV assessment date.
 
For SAEs/AESIs in GSK3745417 monotherapy cohorts:
 
 
• Monotherapy participants who do not crossover: Study Treatment Start Date <math>\leq</math> SAE/AESI Start Date or pre-existing (prior to exposure) SAE/AESI Worsening Date <math>\leq</math> Study Treatment Stop Date + 90 days or Start of Subsequent Anti-Cancer Therapy, whichever occurs first
 
• Monotherapy participants who crossover: Study Treatment Start Date <math>\leq</math> SAE/AESI Start Date or pre-existing (prior to exposure) SAE/AESI Worsening Date <math>\leq</math> the earliest of (Study Treatment Stop Date + 90 days, Start of Subsequent Anti-Cancer Therapy, Crossover Date)
 
• SAE/AESI Start Date is missing
 
 
For SAEs/AESIs in GSK3745417 + dostarlimab combination cohorts:
 
 
• Study Treatment Start Date <math>\leq</math> SAE/AESI Start Date or pre-existing (prior to exposure) SAE/AESI Worsening Date <math>\leq</math> Study Treatment Stop Date + 90 days or Start of Subsequent Anti-Cancer Therapy, whichever occurs first
 
• SAE/AESI Start Date is missing
 
 
For SAEs/AESIs in GSK3745417 + dostarlimab crossover cohorts:
 
 
• (Crossover) Combination Study Treatment Start Date <math>\leq</math> SAE/AESI Start Date or SAE/AESI Worsening Date for SAE/AESI that started during the GSK3745417 monotherapy cohort <math>\leq</math> (Crossover) Combination Study Treatment Stop Date + 90 days or Start of Subsequent Anti-Cancer Therapy, whichever occurs first.
 
• SAE/AESI Start Date is missing
 
 
CCI

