### 6.1.3. Crossover Cohorts

As per Protocol Amendment 6, participants in Part 1A may be considered on a case-by-case basis to transition to a cleared combination dose/frequency regimen as tested in Part 2A.

For participants who cross over to Part 2A from Part 1A, the data occurring prior to crossover will be considered for analysis in the Part 1A cohorts.

For all study population, safety and PK displays, the data occurring after crossover will be included in the applicable displays. In most cases, this will be via the addition of separate crossover combination cohorts (considered the standard approach in this study). When a different approach is required to display the crossover data, details are provided. The approach will be indicated in the programming notes column in Section 12.10 and in the mock shells. For the efficacy table, data occurring after crossover are not included in the display.

The crossover cohorts are labelled according to the subsequent combination therapy dose/regimen. All possible crossover cohorts have been listed in Section 6.1, however, only the crossover cohorts with at least one participant will be included in the displays.

Japan monotherapy participants who cross over to combination therapy will be included in the main study crossover cohorts (that is, there will not be separate Japan crossover cohorts).

The date of crossover is defined as in Section [12.6.4](#).

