## 8.2. Adverse Events Analyses

Adverse events analyses including the analysis of AEs, SAEs and other significant AEs will be based on GSK Core Data Standards. Summary tables will focus on treatment-emergent AEs (TEAEs) only, while listings will include all AEs (not just TEAEs). Details on treatment-emergent AEs are provided in Section 12.4.2 and the derivation for start of subsequent anti-cancer therapy is provided in Section 12.6.2. AEs will be coded using the standard MedDRA dictionary, using the latest version of the standard MedDRA dictionary at the time of the data cut-off, and grouped by system organ class (SOC). AEs will be graded by the investigator according to the Common Terminology Criteria for Adverse Events (CTCAE) version 5.0. All AE displays will include the crossover cohorts, unless otherwise stated. The details of the planned displays are provided in [Appendix 10: List of Data Displays](#).

A TEAE overview summary of the number and percentage of participants with any TEAE, TEAEs related to study treatment, TEAEs leading to permanent discontinuation of study treatment, TEAE leading to dose reduction, TEAE leading to dose interruption/delay, any serious TEAEs, serious TEAEs related to study treatment, fatal serious TEAEs and fatal serious TEAEs related to study treatment will be produced.

TEAEs will be summarized by SOC, preferred term (PT), and maximum grade. The summary (and all similar summaries) will be sorted by SOC in descending order, from the SOC with the highest total incidence (summed across all treatment groups) for any AE within the class to the SOC with the lowest total incidence. The summary (and all similar summaries) will use the following algorithms for counting the participant:

- **Preferred term row:** Participants experiencing the same AE preferred term several times with different grades will only be counted once with the maximum grade.
- **Any event row:** Each participant with at least one AE will be counted only once at the maximum grade no matter how many events they have.

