### 12.6.4. Crossover

The date (and time, where applicable) of crossover is defined as the date (and time) of the first dose of combination therapy for participants who were initially assigned monotherapy.

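### For crossover participants the monotherapy TEAE window can include the first combination dosing day, or run past it, so new combination-period events can be flagged in both cohorts

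*SAP*

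**What the plan says.** SAP 6.1.3 states the allocation principle for participants who move from Part 1A to combination therapy: "the data occurring prior to crossover will be considered for analysis in the Part 1A cohorts". Section 12.6.4 says that crossover "is defined as the date (and time) of the first dose of combination therapy".

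Section 12.4.2 then sets the monotherapy windows for these participants:

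- **Ordinary AEs** (neither SAE nor AESI): the AE start must be no later than "Monotherapy TDV or the earliest of (Monotherapy Study Treatment Stop Date + 30 Days, Crossover Date) if TDV is missing". A note adds: "Note that TDV date is taken as the latest TDV assessment date".
- **SAEs and AESIs**: the start must be no later than "the earliest of (Study Treatment Stop Date + 90 days, Start of Subsequent Anti-Cancer Therapy, Crossover Date").

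The crossover-cohort windows, for both classes of event, open on the combination start date, with that date included.

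For an AE with a known start date, 12.4.2 describes one deliberate double count. It concerns an AE that began on monotherapy and was unresolved at crossover: "If the AE does worsen, then the AE will be counted in both the monotherapy cohort and the crossover combination cohort".

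**The concern.** A new event that starts on or after the first combination dose should count in the crossover cohort only. The 12.4.2 limits allow it to count in Part 1A as well, in two ways.

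- **(a) Shared day.** Where the monotherapy window is limited by the crossover date, that date is included. It is also the first day of the crossover window.
- **(b) Missing limit.** For ordinary AEs the crossover date appears only in the branch for a missing TDV. With a TDV, the window runs to the latest TDV assessment date, even if that falls after combination dosing has begun.

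Incidence and severity of AEs is a primary endpoint (2.2) and is displayed by cohort. The shared day in (a) is the first combination dosing day. CRS is an AESI under 8.2.1, so CRS following the first combination dose could be flagged as monotherapy toxicity too.

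The effect depends on the table:

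- **Participant-based rows** are partly protected: "Participants experiencing the same AE preferred term several times with different grades will only be counted once with the maximum grade". They change only if the participant had no earlier monotherapy event in that row, or none as severe for the grade rows.
- **Occurrence counts** are not protected. In the CRS/IRR table (3.9) and the serious TEAE table (3.10), each overlapping event adds one to Part 1A whatever came before. The table of common non-serious TEAEs (3.5) also counts occurrences.
- **DLT results** are untouched, because 8.2.4 excludes the crossover cohorts from that analysis set.

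**Working it through.** The plan gives no figure to reproduce. The check writes the windows as date limits and counts the start days that satisfy both.

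**Inputs**

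- Day 0 is the last monotherapy dose.
- *g* is the day of crossover, which equals the first combination dose day (12.6.4).
- *t* is the day of the latest monotherapy TDV assessment (12.4.2).
- The limits of 30 and 90 days are from 12.4.2.
- Assumptions: no subsequent anti-cancer therapy before crossover; the stop date in the SAE/AESI rule is the monotherapy stop date; the combination window stays open long enough not to matter.

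**Formula**

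The monotherapy window ends on day *E*, inclusive. The crossover window opens on day *g*, inclusive. Shared days = max(0, *E* − *g* + 1).

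**Results**

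| Branch | *E* | Shared days |
|---|---|---|
| Ordinary AE, TDV missing | min(30, *g*) | 1 if *g* ≤ 30; 0 if *g* ≥ 31 |
| SAE/AESI | min(90, *g*) | 1 if *g* ≤ 90; 0 if *g* ≥ 91 |
| Ordinary AE, TDV present | *t* | *t* − *g* + 1 if *t* ≥ *g*; otherwise 0 |

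A day-by-day enumeration agrees. With TDV missing and *g* from 1 to 120, there is one shared day for all 30 values up to 30 and none for the other 90. For SAEs/AESIs and *g* from 1 to 150, there is one shared day for all 90 values up to 90 and none for the other 60.

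For the TDV branch, with illustrative dates that are not from the SAP:

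| *g* | *t* | Shared days |
|---|---|---|
| 21 | 20 | 0 |
| 21 | 21 | 21 − 21 + 1 = 1 |
| 21 | 28 | 28 − 21 + 1 = 8 |
| 21 | 30 | 30 − 21 + 1 = 10 |
| 28 | 30 | 30 − 28 + 1 = 3 |

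**After the correction**

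Adding the condition that the AE starts before *g*, and keeping the existing inclusive limits, gives 0 shared days in every branch. No whole day before crossover is lost. Making all the limits strict instead would lose one pre-crossover day, so that is not proposed.

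**The case against.** **Section 6.1.3 already settles the allocation.** One can read 12.4.2 as flagging only events that 6.1.3 has already placed in Part 1A. This does not hold well. Section 12.4.2 sets its own crossover limits and its own rule on which cohort counts a worsened AE, so it governs allocation, and a programmer will build the flag from it.

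**Times would break the tie.** Section 12.6.4 allows a crossover time where applicable, and the AE listing in 8.2 carries onset datetime. Comparing datetimes would resolve most of (a), including CRS with a recorded onset after the dose. That much stands. But 12.4.2 is written in dates and gives no tie rule, and times do nothing for (b).

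**Counting an untimed event in both cohorts matches the plan elsewhere.** Section 12.7.2.2 does this for concomitant medication when missing dates leave the period unclear. Here, however, the date is known and only the time is missing. For that situation 12.4.1 has a convention, written for the first dose of study intervention: "first dose date is considered on-intervention for AE and concomitant medication". Following it at crossover has a price: an untimed AE that truly began earlier that day, before the combination dose, is lost from monotherapy.

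**A monotherapy TDV on or after crossover may never occur.** The SAP does not say how often it does, and visit timing is left to the protocol. This is fair, and it is why (b) is conditional. The SAE/AESI rule and the missing-TDV branch both carry the crossover limit, so its absence here looks like an oversight.

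**Redactions.** A block after the SAE/AESI rules in 12.4.2 and the AE partial-date rules in 12.7.2.1 are blacked out. A tie rule there cannot be excluded.

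**Conclusion.** The point holds on the visible text, and the windows should be corrected. A new event can be flagged in both cohorts under these conditions:

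- on the crossover day, for an ordinary AE with no TDV and crossover within 30 days of the last monotherapy dose;
- on the crossover day, for an SAE/AESI with crossover within 90 days and no earlier subsequent therapy;
- from crossover to the TDV, for an ordinary AE with a monotherapy TDV assessment on or after crossover.

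Outside these conditions there is no overlap for events with a known start date. The plan anticipates crossovers inside the 30- and 90-day limits, since taking the earliest of those limits and the crossover date would otherwise serve no purpose.

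The number of misassigned events cannot be stated, because the SAP gives no numbers of crossovers, gaps or TDV timings. Whether an AE with a missing start date is placed by its end date cannot be judged either, and is only a point to check.

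**What to change.** In 12.4.2, for participants who cross over:

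1. Keep the existing inclusive limits: the monotherapy TDV; monotherapy stop + 30 days if the TDV is missing; and, for SAEs/AESIs, the earlier of monotherapy stop + 90 days and the start of subsequent therapy.
2. Add to every dated monotherapy branch, including the one with a TDV, the separate condition: AE start < crossover date/time.
3. If the AE starts on the crossover date and its onset time is missing, assign it to the crossover cohort only, in line with 12.4.1.
4. Leave the worsening exception as it is.
5. Name the stop date in the SAE/AESI rule explicitly as the monotherapy stop date.
6. Check that the AE missing-date rules use the end date in the way 12.7.2.2 does for concomitant medication, and that the redacted text holds no conflicting tie rule.

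The cost is small clarifications of the SAP wording and one added condition in the AE analysis dataset flag, made before database lock. No new data are needed.

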#### 12.7.2.2. Handling of Missing Dates in terms of crossover

This sub-section describes which period (that is, monotherapy or crossover combination therapy) events should be included in for crossover participants when either the start or end date of the event is missing.

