#### Concomitant medication

Note that the only concomitant display to be produced is a listing.

Concomitant Medication Start Date	Concomitant Medication End Date	Cohort Inclusion Rule
Before crossover	Before crossover	Include in monotherapy cohort only
Before crossover	After crossover	Include in both monotherapy and crossover cohort
Before crossover	Missing	Include in both monotherapy and crossover cohort
After crossover	After crossover	Include in crossover cohort only
After crossover	Missing	Include in crossover cohort only
Missing	Before crossover	Include in monotherapy cohort only
Missing	After crossover	Include in both monotherapy and crossover cohort
Missing	Missing	Include in both monotherapy and crossover cohort

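### As SAP 12.4.2 visibly reads, an adverse event with no start date counts as emergent on the crossover combination even if it ended before the first combination dose

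*SAP*

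**What the plan says.** SAP 12.4.2 defines the treatment-emergent flag separately for the monotherapy, combination and crossover cohorts. Each definition has a date window and then, as a separate bullet, the criterion "AE Start Date is missing". The rules for SAEs and AESIs have the same structure, with "SAE/AESI Start Date is missing" under all three cohort types. No visible bullet refers to the end date.

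Three other places bear on the same events:

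- **6.1.3**, on participants who cross over: "the data occurring prior to crossover will be considered for analysis in the Part 1A cohorts".
- **12.4.2, note on a monotherapy AE that is unresolved at crossover**: "If the AE does not worsen, the AE will only be counted in the monotherapy cohort".
- **12.7.2.2**, on missing dates and crossover, opens: "This sub-section describes which period (that is, monotherapy or crossover combination therapy) events should be included in for crossover participants". The only table shown there is for concomitant medication. For a missing start with an end before crossover, its rule is "Include in monotherapy cohort only".

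Section 8.2 shows where the flag is used: "Summary tables will focus on treatment-emergent AEs (TEAEs) only", and "All AE displays will include the crossover cohorts, unless otherwise stated". Section 12.6.4 defines the crossover date as the date of the first combination dose.

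Two blocks that could matter are redacted: the adverse-event row of 12.7.2.1 on missing and partial dates, and a block at the end of the 12.4.2 table.

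**The concern.** Counting an undated event as emergent is a sensible worst-case convention when its timing is unknown. It stops being one when the record itself shows that the event was over before the combination began. On the visible text, such an event appears under the crossover cohort as a combination TEAE and again under monotherapy.

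Incidence and severity of adverse events is a primary endpoint (2.2). A double-flagged event would enter the crossover columns of the TEAE tables, the occurrence counts in Tables 3.5 and 3.10, the pooled Part 2A plus Crossover numerator for the 10% cut-off in Table 3.6, and the all-parts total used for sorting.

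**Working it through.** The plan gives no figure to reproduce. The check applies the visible rules to each combination of dates for a participant who crossed over.

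**Step 1. Can the event in question meet the date window for the crossover cohort?** The window in 12.4.2 requires: first combination dose ≤ event start (or worsening). By 12.6.4, the first combination dose is the crossover date. If the recorded end is before crossover, then start ≤ end < crossover. Whatever the missing start was, it fails the window. Worsening does not rescue it, because any worsening also came before the end date. Only the stand-alone missing-start bullet brings the event into the crossover cohort.

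**Step 2. Compare all cases with the medication table.**

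| Case | Start | End | AE flag, visible 12.4.2 | Medication rule, 12.7.2.2 |
|---|---|---|---|---|
| 1 | Known, on monotherapy | Before crossover | Monotherapy only | Monotherapy only |
| 2 | Known, on monotherapy | After crossover, not worsened | Monotherapy only | Both |
| 3 | Missing | Before crossover | **Both** | Monotherapy only |
| 4 | Missing | After crossover | Both | Both |
| 5 | Missing | Missing | Both | Both |

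The SAE and AESI bullets give the same result in cases 3 to 5.

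**Step 3. Read the table.** Case 3 is out of line in two ways.

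- Against case 2: an event still present when the combination started is kept out of the crossover cohort, while one that had already ended is put in.
- Against the medication column: the medication rule is the more inclusive one in case 2, yet in case 3 it excludes what the AE rule includes.

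Case 3 also contradicts 6.1.3, since an event that ended before crossover occurred wholly before it. Cases 4 and 5 are defensible, because the period cannot be determined from the dates.

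**Step 4. Secondary case, end before the first dose of any study treatment.** The same inequality applies: start ≤ end < first dose, so the event cannot have started on treatment. The missing-start bullet still flags it. The medication table has no row for this case, so this part rests on the logic of the date window alone.

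**The case against.** **Redaction.** The two redacted blocks lie where an end-date check or an imputation rule would be expected. This stands as a limit. A reader might infer that the plan as a whole has no end-date rule for undated events. The documents do not support that; they show only that the visible bullets contain none and refer to none. If hidden imputation fills every start date, the bullets never operate.

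**Section 6.1.3 already allocates the event.** One can read 12.4.2 as flagging only events that 6.1.3 has already assigned to a period, in which case there is no double count. That reading is possible, but 12.4.2 does not state it, and its literal bullet gives the opposite result. The two sections need reconciling, because a programmer working from 12.4.2 alone would flag the event twice.

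**Worst-case handling is deliberate.** The plan also counts missing relatedness as related (8.2.2). This supports cases 4 and 5. It does not support case 3, where the recorded end date rules out emergence on the combination.

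**Limited reach.** Crossover cohorts are outside the DLT evaluable set (8.2.4) and have their own columns and total (Note for Programmers, 12.10.3). The DLT summary and the main Part 2A columns are therefore unaffected. The AE listing prints onset, resolution and the flag, so an affected record can be found. All of this stands and keeps the point minor. A reader might also infer a material inflation of combination incidence. The visible text gives neither crossover cohort sizes nor a count of undated events, so no such size can be stated.

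**Conclusion.** The point holds on the visible text as a minor internal inconsistency. In one definable case (a crossover participant, a missing start date, and a recorded end before the first combination dose), 12.4.2 counts an AE, SAE or AESI in both cohorts. This is contrary to 6.1.3, to its own note on unresolved monotherapy events, and to the end-date logic of 12.7.2.2. The number of affected records is not given and is probably small.

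The conclusion assumes that neither redacted block holds the condition and that some start dates remain missing after any imputation. It does not extend to undated events that end on or after crossover or have no end date.

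**What to change.** In 12.4.2, restrict the missing-start bullets for the crossover cohorts, for AEs and for SAEs/AESIs alike, to events whose end date is missing or on or after the crossover date. Events ending before crossover then count in monotherapy only. Of the five cases above, only case 3 changes.

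As a secondary change, state that an event whose recorded end date is before the first dose of study treatment is not treatment-emergent in any cohort.

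The cost is a sentence or two of text and a simple date condition in the derivation of the flag. The crossover logic already exists for medications, and the AE listing already shows the resolution date. If a redacted passage already imposes the condition, a cross-reference to it in 12.4.2 suffices.

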## NOTES:

- Treatment emergent SAEs/AESIs, as per this definition, are included in the summary tables of TEAEs.
- See Section [12.6.2](#) for definition of start of subsequent anti-cancer therapy.

- Note, if a participant crosses over to combination therapy before an AE is resolved, the actual AE end date should still be populated in the AE listings for the monotherapy cohort (regardless of whether the AE worsened on crossover combination therapy).
- As per the protocol, SAEs that are related to study participation will be collected from the time of consent. Note that these will be included in listings (as listings include all AEs), however, will not be included in the tables (as tables only include treatment related AEs).

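### SAP 12.4.2: when new anti-cancer therapy starts before the ordinary AE window closes, a later SAE or AESI is left out of the TEAE tables while a same-day ordinary AE is counted

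*SAP*

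**What the plan says.** SAP 12.4.2 splits adverse events into two classes with no overlap.

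- **AEs that are neither SAEs nor AESIs.** For monotherapy without crossover, the window ends at the Treatment Discontinuation Visit ("TDV) or Study Treatment Stop Date + 30 Days if TDV is missing"). The combination and crossover cohorts follow the same pattern. New anti-cancer therapy plays no part. On which visit date applies: "Note that TDV date is taken as the latest TDV assessment date".
- **SAEs and AESIs.** The window ends at "Study Treatment Stop Date + 90 days or Start of Subsequent Anti-Cancer Therapy, whichever occurs first". Under 12.6.2, that therapy may start as early as the day of the last dose. It can be an adjudicated systemic therapy or a procedure classed as cancer related.
- **Route into the tables.** Under 8.2, AE summary tables show TEAEs only and listings show all AEs. The notes to 12.4.2 add: "Treatment emergent SAEs/AESIs, as per this definition, are included in the summary tables of TEAEs".
- **Monotherapy period of participants who cross over.** Ordinary AEs end at "Monotherapy TDV or the earliest of (Monotherapy Study Treatment Stop Date + 30 Days, Crossover Date) if TDV is missing". SAEs and AESIs end at "the earliest of (Study Treatment Stop Date + 90 days, Start of Subsequent Anti-Cancer Therapy, Crossover Date"). Section 6.1.3 says that "the data occurring prior to crossover will be considered for analysis in the Part 1A cohorts".

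**The concern.** Stopping the count at new therapy is a defensible way to avoid charging its toxicity to study treatment. That reasoning applies equally to ordinary AEs, yet 12.4.2 does not stop them there. As written, only the more serious class is cut, and nothing visible keeps its window at least as long as the ordinary one.

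Incidence and severity of adverse events is a primary endpoint (SAP 2.2). In participants who switch therapy early, the rule can lower the counts of serious TEAEs, fatal TEAEs, cytokine release syndrome and immune-related events relative to the rule used for ordinary AEs. Because the window ignores causality, an SAE that the investigator judged related could also be missing from the drug-related tables.

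**Working it through.** **Inputs.** Days are counted from the last dose. From 12.4.2, T is the day of TDV, or 30 if TDV is missing, and the SAE/AESI limit is 90. From 12.6.2, d is the day on which new therapy starts, with d at least 0. The SAP gives no actual values of T or d, so those below are assumptions, except T = 30 for a missing TDV.

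**Rules as written.** An ordinary AE with onset day s counts if s ≤ T. An SAE/AESI counts if s ≤ min(90, d), so an event on the day therapy starts still counts.

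**Days on which an ordinary AE counts and an SAE/AESI does not** = max(0, T − min(90, d)):

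| | d = 0 | d = 10 | d = 20 | d = 30 |
|---|---|---|---|---|
| TDV missing (T = 30) | 30 | 20 | 10 | 0 |
| TDV on day 14 | 14 | 4 | 0 | 0 |
| TDV on day 45 | 45 | 35 | 25 | 15 |

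For example, with T = 30 and d = 10 the gap is 30 − 10 = 20 days (days 11 to 30). A gap opens only if d < T.

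**The other direction.** Extra SAE/AESI days = max(0, min(90, d) − T). With T = 30, therapy on day 45 gives 45 − 30 = 15 extra days, and no new therapy gives 90 − 30 = 60.

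**Worked case.** Suppose therapy starts on day 10, a fatal SAE begins on day 15, death follows on day 20, and TDV is missing. The SAE fails 15 ≤ min(90, 10) = 10, so it is absent from the fatal serious TEAE counts in Tables 3.1 and 3.10. A non-serious, non-AESI event on day 15 passes 15 ≤ 30 and is tabulated. The death is in Table 3.17 as within 30 days of last dose.

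**With a floor.** The SAE/AESI end becomes max[T, min(90, d)]. This is never below T, so the gap is 0 for every T and d. It is never below min(90, d), so no SAE or AESI now tabulated is lost. The 15 and 60 extra days are unchanged.

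**Crossover, conditional on a monotherapy TDV after crossover.** With crossover on day c and no other therapy, the ordinary end is TDV when present and the SAE/AESI end is min(90, c). For an assumed TDV on day 28, the ends differ by 28 − c days: 21, 14, 7 and 0 for c = 7, 14, 21 and 28.

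**Scale, as illustration only.** If the excluded event were a participant's only serious TEAE, the rate would move by 1/3 (33 points) in a cohort of 3 or 1/9 (11 points) in a cohort of 9.

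**The case against.** The case on the other side has five parts.

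- **The SAE/AESI rule may be the intended one.** It is stated in the same way for each cohort and matches follow-up under Amendment 7, which ends at 90 days or at new therapy (SAP 3.3, 7.2). Cutting ordinary AEs at new therapy would align the classes just as well. This stands as a point about the choice of remedy. It does not explain why only one class is cut.
- **Redaction.** Blacked-out text follows the definitions in 12.4.2, and the date-handling rows in 12.7.2.1 are also hidden. A floor could be there. This stands as a limit on confidence.
- **No demonstrated effect.** The SAP does not show how often therapy precedes TDV, or that SAEs were collected after new therapy. Before Amendment 7 the required follow-up was two years from first dose, so collection is plausible for earlier participants but not shown. This limits the size of the point.
- **Section 12.4.1 is a weak benchmark.** A reader might infer that the rule is wrong because it conflicts with the on-intervention phase, which "is defined as time from first dose to last dose plus 30 days". Ordinary AEs already depart from that phase whenever TDV is not on day 30. With TDV on day 14 and therapy on day 10, the floored window ends at max(14, 10) = 14, so an SAE on days 15 to 30 stays on-intervention but unflagged. The floor secures agreement with 12.4.1 only if TDV is missing or on day 30 or later, so that is not the reason for it.
- **Table 3.17 need not match.** It counts all deaths without a treatment-emergence condition, so a difference from the fatal TEAE counts is not in itself a contradiction. The floor restores the day-15 event only if TDV is missing or on day 15 or later. With TDV on day 14, an ordinary AE on day 15 would be excluded too.

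**Conclusion.** The inconsistency is real on the visible text and should be corrected. It is confined to SAEs and AESIs that begin after an early start of new therapy but within the ordinary AE window. The gap per affected participant is T − d days, at most 30 when TDV is missing and longer only if TDV falls later than day 30. The number of participants and events affected cannot be derived.

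Two stronger readings are not supported. A reader might infer that SAEs and AESIs generally have the shorter window; without new therapy theirs is 60 days longer when TDV is missing. A reader might also infer that serious events disappear from the report; they remain in the listing of all AEs with the flag shown, and every death remains in Table 3.17.

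The crossover mismatch is secondary. It arises only if a monotherapy TDV can fall after the crossover date, which the SAP does not show. It loses no SAE through the crossover cap, because an SAE starting from that point is assessed under the crossover cohort's own window.

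Confidence is moderate because of the redactions.

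**What to change.** First check whether the redacted text after the definitions in 12.4.2 already sets a floor. If it does not, flag an SAE or AESI as treatment-emergent when it starts on or before

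max[TDV, or stop + 30 days if TDV is missing; min(stop + 90 days, start of subsequent anti-cancer therapy)].

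Give consistency between the two event classes as the reason. Leave 12.6.2 and the 90-day extension as they are. The floor is preferable to cutting ordinary AEs at new therapy because it removes no event now tabulated.

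If a monotherapy TDV can fall after crossover, also end the ordinary AE window of the monotherapy period at the crossover date, as is already done for SAEs and AESIs and in line with 6.1.3. Ordinary AEs between crossover and that TDV would leave the monotherapy column; those inside the combination window still count in the crossover column.

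The cost is one sentence and one line of flag derivation, and the same again for the crossover cap, with no new data collection. The downside is that some SAEs and AESIs after an early switch enter the tables. Where causality is missing, 8.2.2 treats an SAE as related, so such events would also enter the drug-related serious tables.
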